4 STUDY DESIGN

4.1 OVERALL DESIGN

We plan to conduct a single-site cluster RCT of 20 acute care nursing units in the main Medical Center to compare use of the SAFE Loop (intervention nursing units) and an existing incident reporting system (control nursing units). Implementation of the intervention will be sequential in two phases (5 intervention and 5 control units will be randomized at a time). Randomization will occur in blocks to assure the similarities of the nursing units, with 4 nursing units per block, matched on patient population, size of the nursing unit, and other factors.

Corresponding to three study Aims above, outcome measures include:

- (Aim 1) incident reporting practices (rates at which nurses report high-priority medication incidents and numbers of contributing factors described per report),
- (Aim 2) nurses’ attitudes toward incident reporting (AHRQ Hospital Survey on Patient Safety Culture™, particularly perceptions of feedback and communication about error and of the frequency with which events are reported), and
- (Aim 3) rates of high-priority medication events (determined via IHI Trigger Tool method of medical record review).

Analyses will compare changes in outcomes between from before to after implementation in intervention and control arms. Qualitative interviews of nurses the SAFE Loop intervention arm will provide insight into implementation.

To minimize bias while also facilitating study feasibility, randomization will be done at the nursing unit level, and research staff involved in data collection will not have access to information on which nurses and patients were assigned to which arm. Also to minimize bias, nurses participating in the survey in Aim 2 will be informed that the results will be analyzed as part of a study on patient safety and incident reporting, without specifically linking the survey to the SAFE Loop study.

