9 STATISTICAL CONSIDERATIONS

9.1 STATISTICAL HYPOTHESES

Aim 1 Hypotheses:

1.1 The rate per 1000 patient-days at which nurses report incidents will increase more in nursing units engaged in the SAFE Loop than in units using the existing reporting system.

1.2 The number of system plus human factors per incident report will increase more in nursing units engaged in the SAFE Loop than in units using the existing reporting system. (Primary outcome for Aim 1)

Aim 2 Hypotheses:

2.1 Nurses' perceptions of feedback and communication about error on the nursing unit will improve more in nursing units engaged in the SAFE Loop than in units using the existing reporting system. (Primary outcome for Aim 2)

2.2 Nurses' perceptions of the frequency with which events are reported on the nursing unit will increase more in nursing units engaged in the SAFE Loop than in units using the existing reporting system.

Aim 3 Hypotheses:

3.1 The rate of medication events designated as high priorities will decline more in nursing units engaged in the SAFE Loop than in units using the existing reporting system. (Primary outcome for Aim 3)

3.2 The rate of medication events designated as high priorities and involving harm will decline more in nursing units engaged in the SAFE Loop than in units using the existing reporting system.

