9.2 SAMPLE SIZE DETERMINATION

Aim 1:

On average per 6-month study period, each unit will provide 7,362 patient-days of care (294,470 pt-days/20/2) and submit 16.6 reports (665 reports/20/2). *H1.1.* The baseline rate is 2.26 incident reports per 1000 patient-days (665 reports/294,470). *H1.2.* Based on prior studies, the expected baseline number of system plus

Table 1: Minimum Detectable Difference in Outcome				
Implementation trend	Betw-Cluster Coeff. of Variation			
	0.01	0.05	0.10	0.20
1.1. Incident Reports per 1000 Patient-days				
Yes	1.241	1.277	1.392	1.851
No	0.794	0.815	0.877	1.115
1.2. System plus Human Factors per Incident Report				
Yes	0.471	0.481	0.515	0.651
No	0.299	0.305	0.322	0.391

human factors is 0.70 per report.¹ **Table 1** presents the minimum detectable differences in outcomes as functions of the between-cluster coefficient of variation (CV) and the presence of implementation trend, using two-sided t-tests for Poisson rates with 80% power at 5% significance level. These differences would be meaningful to safety leaders, reflecting >35% increases in reporting rates and enhanced detection of the multiple contributing multiple factors that are typically involved in every error.

Aim 2:

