9.4.2 ANALYSIS OF THE PRIMARY EFFICACY ENDPOINT(S)

Aim 1 Analyses:

Descriptive Analysis: We will perform descriptive analyses of reporting practices during the baseline periods and intervention periods, stratified by study arm. We will calculate rates of reported Target Medication Events and total reported medication events per 1000 patient-days (# of reports*1000/# of patient-days). Next, we will calculate the percentages of reported incidents in each NCC MERP category and the percentages of reports for which preventability could be determined. Finally, we will calculate

the number of contributing system, human, and patient factors per report and describe the types of factors reported.

Statistical Analyses: We will compare changes over time between study arms for: (a) rate of incident reports per 1000 patient-days, and (b) number of system plus human factors per report. Multivariable Poisson regression models will be fitted with response variables as (a) number of reports per patient, with offset given by the length of stay divided by 1000; and (b) number of system plus human factors per report. For both models, the main hypothesis is whether there is an interaction between study arm and time period (baseline, post-intervention). Nursing units will be divided between two implementation steps, creating the possibility of an implementation trend. Therefore, a three-way interaction among study arm, time period, and implementation step (Step 1: Group 1 and 2, Step 2: Group 3 and 4) will be tested. If this is statistically significant, results will be presented separately for each implementation step. Otherwise, implementation step will be an additive effect. Random effects will describe nursing units and models will adjust for demographics, Elixhauser comorbidity index, and primary payer (collected under Aim 3). All hypotheses will be two-sided at 5% significance level. Calculations will be performed in R-package, version 3.5.3.

Aim 2 Analyses:

Descriptive Analysis: We will calculate survey response rates, examine respondent characteristics (years worked in current profession, hospital, and current nursing unit and hours worked per week), and describe outcome measures (overall scores and composite measures) during each study period, stratified by study arm.

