Assessment of Survey Measurement Properties: To evaluate the two selected composite measures' internal consistency, we will calculate Cronbach's α using data from baseline survey. To assess construct validity and convergent validity, respectively, we will evaluate associations (Pearson correlation coefficients) between scores on the composite measures and: (1) the full Hospital SOPS, and (2) incident reporting rates at the nursing unit level. To assess responsiveness, we will compare scores from baseline and follow-up surveys among nurses in the SAFE Loop arm (paired t-tests). If the composite measures do not demonstrate good internal consistency, construct, and convergent validity, we will use the full Hospital SOPS.

Statistical Analyses: We will compare changes over time between study arms for Feedback and Communication About Error and Frequency of Events Reported. Multivariable Normal regression models will be fitted for both endpoints and we will test hypotheses similarly to Aim 1. We will adjust for nurse characteristics from the AHRQ survey: years working in this hospital, years worked in current nursing unit, and hours worked per week. We will perform subgroup analyses by years of experience in current profession, because experience has been associated with medication error rates.⁵⁹

Aim 3 Analyses:

Descriptive Analysis: We will calculate rates of preventable ADEs and potential ADEs per 1,000 patient-days, both overall and for the Target Medication Events for the Group 1 and 3 nursing units. We will describe the severity of the events, medication classes, errors, clinicians involved, and stages in drug therapy.

Statistical Analysis: We will compare changes over time between study arms for rates of (a) Target Medication Events per 1000 patient-days and (b) harmful Target Medication Events per 1000 patient-days. Multivariable Poisson models will be fitted with response variable as the number of (a) target medication events and (b) harmful medication events, with offset the length of stay divided by 1000

days. We will test hypotheses similarly to under Aim 1. Model covariates will include patient demographics, biological sex, Elixhauser comorbidity index, and insurance payer.

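### The arm-by-period interaction for H1.2 is a valid test, but it gives up about 14 to 23 points of power that a common-baseline model would recover; for the Aim 2 survey outcomes the gain is small and uncertain

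*Combined protocol and SAP*

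**What the plan says.** Section 4.1 sets the general approach: "Analyses will compare changes in outcomes between from before to after implementation in intervention and control arms". Section 9.1 words the Aim 1 primary hypothesis the same way: "The number of system plus human factors per incident report will increase more in nursing units engaged in the SAFE Loop".

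Section 9.4.2 (Aim 1, Statistical Analyses) turns this into a Poisson regression and names the test: "For both models, the main hypothesis is whether there is an interaction between study arm and time period (baseline, post-intervention". The remaining terms are these: "Random effects will describe nursing units and models will adjust for demographics, Elixhauser comorbidity index, and primary payer". Implementation step enters as an additive effect unless its three-way interaction with arm and period is significant.

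For Aim 2 the same section says "We will compare changes over time between study arms for Feedback and Communication About Error and Frequency of Events Reported", and adds that "we will test hypotheses similarly to Aim 1", with nurse characteristics as covariates.

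No section uses a unit's baseline outcome as a covariate or constrains the arms to a common baseline mean.

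**The concern.** An arm-by-period interaction estimates two things: the arm difference after implementation and the arm difference at baseline. It then subtracts the second from the first. In a non-randomised comparison that subtraction removes confounding. Here units are randomised within blocks, and section 6.3 has the envelopes opened only at the start of each implementation period, after that step's baseline. The expected baseline difference is already zero, so the subtraction removes no bias and brings in the sampling error of the baseline means.

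That error is large for H1.2, because each unit contributes few reports per period. The number of units is fixed at 20, so the choice of contrast is one of the few ways left to gain precision. At stake is the chance of detecting a real improvement in report quality, the primary outcome of Aim 1.

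**Working it through.** **Inputs (section 9.2).** Baseline mean 0.70 factors per report. Per period, units "submit 16.6 reports (665 reports/20/2"). CV is 0.01, 0.05, 0.10 or 0.20, with none chosen. There are 20 units, 10 per arm. Table 1 is stated as "using two-sided t-tests for Poisson rates with 80% power at 5% significance level". For Aim 2: SD 37 points, 50.5 responses per unit per deployment, meaningful difference 8.6 points.

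**1. Reproducing Table 1.** The cluster-trial formula for Poisson rates is c = 1 + (1.96 + 0.84)² × [(λ0+λ1)/y + CV²(λ0²+λ1²)] / (λ1−λ0)², with y = 16.6. At CV 0.10 and difference 0.322 (λ1 = 1.022):
- (0.70+1.022)/16.6 = 0.1037
- 0.01 × (0.490+1.044) = 0.0153, so the sum is 0.1191
- c = 1 + 7.849 × 0.1191/0.1037 = 10.0 units per arm

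With c = 10 the formula returns the row without implementation trend (0.299, 0.305, 0.322, 0.391). With c = 5 it returns the row with trend. The formula compares post-period rates and has no baseline term.

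**2. Why the change contrast is noisier.** Let r be the correlation between a unit's baseline and follow-up means. The change contrast has variance proportional to 2(1−r), and the adjusted contrast to 1−r². The ratio is 2/(1+r), which exceeds 1 whenever r < 1. For H1.2, r = (0.70·CV)² / [(0.70·CV)² + 0.70/16.6], where 0.70/16.6 = 0.0422.

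| CV | r | variance ratio | SE ratio |
|---|---|---|---|
| 0.01 | 0.001 | 2.00 | 1.41 |
| 0.05 | 0.028 | 1.95 | 1.39 |
| 0.10 | 0.104 | 1.81 | 1.35 |
| 0.20 | 0.317 | 1.52 | 1.23 |

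**3. Power at the Table 1 differences (rate scale, normal approximation).** The change variance is [(3λ0+λ1)/y + CV²(λ1−λ0)²]/9. At CV 0.10 this is (0.1881+0.0010)/9 = 0.0210, so SE = 0.145, 0.322/0.145 = 2.22, and power = Φ(2.22−1.96) = 60%. Over the four CVs the change test has 55%, 56%, 60% and 75%; the adjusted contrast has 80%, 80%, 80% and 85%. On the log scale, which is the usual Poisson link, the change test has 47%, 49%, 52% and 66%, against 80%, 80%, 80% and 85%. A simulated Poisson mixed model with a unit random intercept (400 runs per setting) gave 47% against 83% (CV 0.01), 55% against 86% (0.10) and 70% against 92% (0.20). Type I error was 4% to 5.5% for the interaction and 3% to 4% for the common-baseline test.

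**4. Unit-level simulation at one fixed effect.** With a true increase of 0.322 and weighted t-tests on 20 units:

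| CV | change | adjusted | gain |
|---|---|---|---|
| 0.01 | 59% | 82% | 23 |
| 0.05 | 59% | 81% | 22 |
| 0.10 | 59% | 79% | 20 |
| 0.20 | 59% | 73% | 14 |

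Type I error is about 5% for both tests. These runs fit an effect that is the same in every unit. In a repeat with the effect proportional to the unit's own rate, the CV 0.20 gain was nearer 10 points (58% against 69%). At CVs assumed beyond the plan's range the gain is about 5 to 10 points at 0.30 and 0 to 5 at 0.40.

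**5. Aim 2 at 8.6 points.** Let T = ICC + (1−ICC)/50.5 and r = [s·ICC + q(1−ICC)/50.5]/T. Here s is the share of unit variance that is stable between deployments, and q is nurse overlap times within-nurse correlation. The documents give neither, so both are assumed. The change variance is (2/10)·37²·T·2(1−r), with 17 df. The adjusted variance is (2/10)·37²·T·(1−r²)·(16/15), with 16 df; the factor 16/15 allows for estimating the slope. Power, change → adjusted:

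| ICC | s=1, q=0 | s=0.8, q=0 | s=1, q=0.40 |
|---|---|---|---|
| 0.01 | 70→83% | 65→81% | 89→93% |
| 0.05 | 71→75% | 53→60% | 90→91% |
| 0.10 | 74→74% | 43→47% | 92→91% |
| 0.20 | 79→77% | 31→33% | 94→93% |

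Allowing for simulation and formula variants, this is about 5 to 15 points at ICC 0.01, 0 to 9 at 0.05, and close to nil (within a few points either way) at 0.10 to 0.20.

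**The case against.** **The planned test is not an error.** This stands. It controls type I error and matches the hypotheses as worded. A reader might infer that the interaction is biased or invalid; nothing in the documents supports that. With equal expected baselines both contrasts estimate the same effect, and the point is efficiency only.

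**A single figure of about 20 points is not general.** This stands. The size depends on a CV that section 9.2 leaves open, and the units range from the emergency department to neonatal intensive care. Losing half the information requires a CV near 0.01.

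**Aim 2 should not share the H1.2 claim.** This largely stands. Sections 5.1 and 8.1 have largely the same nurses surveyed twice, which raises r and shrinks the gain. Low absolute power at ICC 0.05 to 0.10 appears only if unit effects are assumed unstable, which the documents do not say. A reader might infer a substantial loss for H2.1; that is not supported beyond ICC 0.01.

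**Unit-level tests are not the planned model.** True. The mixed-model simulation shows gains at least as large, so the direction holds, but the exact powers differ. A unit-level regression would also drop the prespecified patient and nurse covariates.

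**Target Events may reach H1.2.** This is partly right. Section 9.2 uses the same 665 reports for H1.1, which sections 3 and 8.1 define by Target Events, and for H1.2. Section 8.1 has analysts review medication reports generally. If H1.2 were restricted to Target Event reports, whose definitions the intervention units choose, exchangeable baselines could not be taken for granted.

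**Conclusion.** The point holds for H1.2 as a loss of efficiency. Over the plan's own CV range the baseline-adjusted contrast adds about 14 to 23 points of unit-level power for a true increase of 0.322, and less if CV exceeds 0.20 or the effect scales with the unit's rate. This rests on the Table 1 inputs, unit effects that are stable between periods, and H1.2 being computed on all medication incident reports.

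For H2.1 and H2.2 the gain is small and uncertain, and may be zero or slightly negative at high ICC. Changing them is a matter of consistency. A reader might extend the argument to H1.1 or Aim 3 because they use the same test. That does not follow, since the intervention units choose the events being counted.

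**What to change.** In section 9.4.2, make the primary test for H1.2 the arm-by-post term in the planned mixed model with a common baseline mean: period plus arm-by-post, no arm main effect. Keep implementation step, unit random effects and the prespecified patient covariates. For consistency, use the same form for H2.1 and H2.2 with the planned nurse covariates. Keep the arm-by-period interaction as a sensitivity analysis.

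State that H1.2 is computed on all medication incident reports when this constraint is used. Do not apply it to Target Event outcomes (H1.1, H3.1, H3.2). Do not replace the interaction by a post-only comparison: for Aim 2, without baseline, that is weaker than the interaction from ICC 0.05 upwards (51% against 76% at ICC 0.05 by normal approximation, with stable unit effects and independent respondents).

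The cost is SAP wording, with no new data. The downside is that the constraint relies on exchangeable baselines, which the sensitivity analysis helps to probe. A unit-level version would cost one degree of freedom. The change should be made before outcomes are analysed by arm.

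### A 5% test of the arm by period by step interaction decides which primary result is given; if either step can then count as a finding, the false-positive rate per outcome is about 8%, and no overall answer is provided for after a split

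*Combined protocol and SAP*

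**What the plan says.** The scheme is set out under the Aim 1 statistical analyses in section 9.4.2. For both Aim 1 models, "the main hypothesis is whether there is an interaction between study arm and time period (baseline, post-intervention"). Because the units enter in two steps, "a three-way interaction among study arm, time period, and implementation step (Step 1: Group 1 and 2, Step 2: Group 3 and 4) will be" put to a significance test. Two branches follow. In the first, "If this is statistically significant, results will be presented separately for each implementation step". In the second, "Otherwise, implementation step will be an additive effect". The level is the same throughout: "All hypotheses will be two-sided at 5% significance level".

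Aim 2 adopts the scheme ("Multivariable Normal regression models will be fitted for both endpoints and we will test hypotheses similarly to Aim 1"), and so does Aim 3 ("We will test hypotheses similarly to under Aim 1"). It therefore governs all three primary outcomes listed in section 9.1.

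Section 4.1 gives the size of each step: "5 intervention and 5 control units will be randomized at a time". A step-specific comparison is thus 5 against 5 units, and the pooled comparison is 10 against 10.

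Three things are not stated anywhere in the plan: how the 5% is shared between two step-specific results, what counts as success for an aim once results are split, and whether the pooled effect is still tested and reported as primary in that case.

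**The concern.** The choice between one pooled test and two step-specific tests is made by a significance test on the same data. When the first branch is taken, two chances at 5% replace one. They arise in a selected set of datasets, because a significant three-way interaction means that the two step effects are far apart. With no true effect anywhere, a wide gap makes it likely that at least one step differs significantly from zero. Counting only how rarely the split occurs therefore understates the problem.

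Two things are at stake. The first is whether the stated 5% holds for each outcome. The second is whether each aim is sure to end with a single answer to its main hypothesis.

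**Working it through.** **1. How the plan itself treats a split.** Table 1 in section 9.2 gives minimum detectable differences with and without an implementation trend, at 80% power and two-sided 5%. They can be reproduced with the Hayes-Bennett formula for cluster-randomised rates:

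(c − 1) d² = (1.960 + 0.842)² × [ (λ0 + λ1)/y + CV² (λ0² + λ1²) ], with λ1 = λ0 + d and (1.960 + 0.842)² = 7.849.

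Inputs from section 9.2:
- H1.1: λ0 = 2.26 per 1000 patient-days and y = 7.362 thousand patient-days per unit per period.
- H1.2: λ0 = 0.70 factors per report and y = 16.6 reports per unit per period.
- CV is the between-cluster coefficient of variation.

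Example, H1.2 at CV 0.10:
- c = 5 per arm: 7.849 × (0.1153 + 0.0197) / 4 = 0.265, so d = 0.515. Table 1 with trend gives 0.515.
- c = 10 per arm: 7.849 × (0.1038 + 0.0154) / 9 = 0.104, so d = 0.322. Table 1 without trend gives 0.322.

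All 16 entries of Table 1 reproduce to within 0.001, with c = 5 for the trend rows and c = 10 for the others. The trend rows are therefore what a step-specific 5 against 5 comparison at the full 5% would give, with no allowance for there being two of them.

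**2. False-positive rate of the rule.** Let Z1 and Z2 be the step-specific test statistics. With no effect in either step, and with equally precise and independent steps, both are standard normal. Define
- pooled statistic P = (Z1 + Z2)/√2
- three-way interaction statistic D = (Z1 − Z2)/√2

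P and D are independent. The rule uses P when |D| ≤ 1.96, and Z1 and Z2 otherwise.

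- Pooled branch: 0.95 × 5% = 4.75%.
- Split branch, either step counts: the branch is reached 5% of the time. By numerical integration, at least one of |Z1|, |Z2| then exceeds 1.96 in 65.0% of cases. Contribution: 5% × 65.0% = 3.25%.
- Total: 4.75% + 3.25% = **8.0%**.
- Split branch, both steps required: 2.5% of splits qualify, contributing 5% × 2.5% = 0.125%. Total: 4.75% + 0.125% = **4.9%**.

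**3. Sensitivity of the 8.0% (either step counts).**

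| Variation | False-positive rate |
|---|---|
| Monte Carlo, 4 million draws | 8.0% |
| Unit-level t-tests, 5 against 5, separate step models (8 df) | 7.9% |
| Unit-level t-tests, joint model (16 df) | 8.2% |
| Information split 30:70 between steps | 8.1% |
| Each step tested at 2.5% after a split | 6.9% |
| Favourable direction only | 4.1% against a nominal 2.5% |

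**4. Power under the same two success rules.** Take a common true effect for which the pooled test has 80% power, with no true trend.
- Either step counts: at least one step is significant in 98.9% of splits. Overall power is 0.95 × 80% + 5% × 98.9% = 80.9%.
- Both steps required: 1.4% of splits qualify. Overall power is 0.95 × 80% + 5% × 1.4% = 76.1%.

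**5. How often there is a split with no true trend.** It occurs in 5% of analyses per outcome. If the three primary outcomes were independent, at least one would be split in 1 − 0.95³ = 14.3% of trials.

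**The case against.** The strongest reply is that the plan promises only to present results by step. It does not say that one significant step is a positive finding. The hypotheses in section 9.1 are all overall comparisons of the SAFE Loop with the existing system, and the 5% sentence can be read as covering those alone. This stands to the extent that 8.0% is conditional on an unstated success rule and should not be quoted as a fixed property of the design. It does not dispose of the point. No other rule is written, and Table 1 treats the trend case exactly as step-specific testing at an unadjusted 5% would.

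A reader might infer that the pooled estimate is suppressed after a split. The documents do not say so: the arm by period interaction is named the main hypothesis without condition, and nothing forbids reporting it as well. What can be said is that the pooled model is described only as the alternative to the split, so the plan does not provide for an overall answer in the other branch.

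A reader might also infer a hidden loss of power. That is not supported alongside the 8.0%. Under the rule that gives 8.0%, overall power is 81%; the fall to 76% belongs to the rule that gives 4.9%. In addition, section 9.2 openly tabulates the larger detectable differences under a trend.

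Finally, the split is pre-specified and has a stated reason, and showing step results when they differ is a defensible wish. That is fair, and the change below keeps those results.

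**Conclusion.** The point holds in a conditional form. The plan lets a 5% pre-test choose the form of the primary result for every aim, without controlling alpha across the branches and without a success rule for one of them. If significance in either step counts, the false-positive rate per outcome is about 8.0% (7.9% to 8.2% across the variations that keep 5% per step and count both directions). If both steps are required, it is 4.9%, at the cost of about 4 percentage points of overall power. Under either rule, 5% of analyses per outcome reach the split with no true trend, and the plan then provides for no overall answer to its main hypothesis.

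The figures assume that the two steps are independent, that they carry about equal information (10 units each, with 30:70 changing little), and that each single test holds its nominal 5%. Whether the planned mixed models do so with 20 units is a separate question. The matter should be settled before outcome data are seen.

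**What to change.** Amend the Aim 1 text in section 9.4.2, and the sentences that carry it to Aims 2 and 3, to say that:

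- the pooled arm by period effect is always tested at two-sided 5% and reported as the primary result for each aim, whatever the three-way interaction shows;
- the three-way interaction and the step-specific estimates, with confidence intervals, are a pre-specified heterogeneity analysis that supports no separate 5% claims.

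This returns the rate to 5.0% per outcome, guarantees an overall answer, and still shows any implementation trend. Keeping the split and testing each step at 2.5% would not be enough, since the rate would still be 6.9%. The cost is a change of wording, with no new data or units.

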- Aim 2 (Survey): Nurses will be eligible for survey administration if they worked >50% time on one study nursing unit during a 6-month study period; this will ensure adequate exposure to the study conditions and the opportunity to complete baseline and follow-up surveys. About 1,980 nurses will be eligible.
- Qualitative analysis of implementation: Nurse unit managers and nurses will be eligible for the qualitative interview if they worked at least 50% time on the study nursing units for the entire duration of a SAFE Loop implementation period. (We will enroll 32 participants out of a pool of approximately 800 eligible nurses.)

Patients:

Cedars-Sinai has a total of 294,470 patient-days of care in eligible nursing units per year. Patients located in experimental and control group nursing units will be eligible for participation. If patients transfer between nursing units during the study, analyses will allocate each day of the hospitalization to the unit where the patient was that day. For the review of medical records under Aim 3, we will randomly select 1,520 patients hospitalized during the baseline and follow-on periods.

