Power calculations are the same for both composite outcome measures. The baseline percentages of positive responses are 75% (H2.1) and 72% (H2.2). We assume 85% of 1980 nurses will be eligible and a 60% response rate (50.5 responses per nursing unit per deployment). We also assume a discrete uniform distribution for each composite measure with only four possible values (0%, 33%, 66%, 100%) per nurse because each measure contains 3 items. Therefore, we assume standard deviation (SD) equal to 37%, and a between-cluster coefficient of variation of 0.65 as recommended by Campbell and Walters.² The **Table** presents the minimum detectable difference in the percentage of positive responses as a function of the intra-cluster correlation (ICC) and presence of implementation trend, using a two-sided t-test for Normal means with 80% power at 5% significance level. Based on prior studies, a meaningful difference in the percentage of positive responses is 8.6 percentage points (pp).³ Missing data patterns will be examined using the method proposed by Little⁴ if the data is found to be not missing at completely random, missing values will be imputed with values drawn from fully conditional specifications using the multivariate imputation by chained equations (MICE) algorithm,^{5,6} with the number of imputed datasets chosen such that the maximum loss of efficiency of 5%.⁷ The plausibility of imputed values will be checked by corresponding diagnostics. The outlined statistical analysis will be performed for each imputed dataset and results will be pooled. All hypotheses will be two-sided at 5% significance level. Calculations will be performed using R-package, version 3.5.3.

Implementation trend	Intra-cluster Correlation			
	0.01	0.05	0.10	0.20
Yes	10pp*	11pp	12pp	13pp
No	7pp	8pp	10pp	11pp

¹ [name] TK, Bell DS, Paddock SM, Hilborne LH. Contributing factors identified by hospital incident report narratives. Qual Saf Health Care. Oct 2008;17(5):368-372.

² Campbell MJ, Walters SJ. How to design, analyse and report cluster randomised trials in medicine and health related research. John Wiley & Sons; 2014.

³ Campione J, Famolaro T. Promising Practices for Improving Hospital Patient Safety Culture. Jt Comm J Qual Patient Saf. Jan 2018;44(1):23-32.

⁴ Little RJ. A test of missing completely at random for multivariate data with missing values. Journal of the American Statistical Association. 1988;83(404):1198-1202.

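### Section 9.4.2 leaves the nursing-unit random-effects structure for H2.1 open; fitted as a unit intercept with a Wald z test, its true level need not be 5%

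*Combined protocol and SAP*

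**What the plan says.** Section 9.4.2 sets out the testing under Aim 1: "the main hypothesis is whether there is an interaction between study arm and time period (baseline, post-intervention"), two-sided at 5%. Clustering is covered by "Random effects will describe nursing units". For Aim 2 the plan adds "Multivariable Normal regression models will be fitted for both endpoints and we will test hypotheses similarly to Aim 1", and on covariates "We will adjust for nurse characteristics from the AHRQ survey". It names no intercept, unit-by-period or nurse term, no test statistic and no degrees-of-freedom method. A three-way test of arm, period and implementation step comes first; if it is significant, results are given by step.

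Section 9.2 sizes Aim 2 as follows: "We assume 85% of 1980 nurses will be eligible and a 60% response rate (50.5 responses per nursing unit per deployment"), with an SD of 37 percentage points. It tabulates the "minimum detectable difference in the percentage of positive responses as a function of the intra-cluster correlation (ICC) and presence of implementation trend", for ICC 0.01 to 0.20, "using a two-sided t-test for Normal means with 80% power at 5% significance level". Section 5.1 justifies the eligibility rule in that "this will ensure adequate exposure to the study conditions and the opportunity to complete baseline and follow-up surveys", so many nurses may answer twice.

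**The concern.** The H2.1 effect is a difference between arms in within-unit change. A unit intercept is common to both periods and cancels from that change. What remains is (a) any movement of a unit's true level between surveys and (b) response-level noise. An intercept-only model estimates (b) as if all responses were independent and gives (a) no term. Omitting (a) makes the standard error too small. Ignoring nurses who answer both surveys makes it too large. The net error depends on drift, ICC and overlap.

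At stake is the stated 5% level of the Aim 2 primary test. H2.2 has the same wording and the same exposure. Two competent analysts could fit different models from this text and reach different conclusions.

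**Working it through.** **Inputs from the plan.** Section 9.2: 1,980 nurses, 85% eligible, 60% response, SD 37, ICC 0.01 / 0.05 / 0.10 / 0.20, meaningful difference 8.6 points. Sections 6.3 and 9.3: 20 units, 10 per arm. Section 5.1 table: nurses per unit.

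**Assumed, not in the documents.** r is the between-period correlation of a unit's true level that remains after covariates. f is the share answering both surveys times the within-nurse correlation. Both are shown as ranges.

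**Step 1: the plan's own figures.** Responses per unit and deployment: 1980 × 0.85 × 0.60 / 20 = 50.49, as stated. The SD of a uniform distribution on 0, 33, 67 and 100 is 37.3, also as stated. The detectable-difference row without implementation trend (7 / 8 / 10 / 11 points) does not reproduce:
- Intercept-only difference in differences, 2.80 × 37 × √[4(1 − ICC)/(10 × 50.49)]: 9.2 / 9.0 / 8.7 / 8.2, falling with ICC.
- Post-period comparison only, 2.80 × 37 × √[2(1 + 49.49 × ICC)/(10 × 50.49)]: 8.0 / 12.2 / 15.9 / 21.5.

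**Step 2: true against modelled variance.** With m = 50.49:
- True variance of the contrast: 37² × 4[ICC(1 − r) + (1 − ICC)(1 − f)/m]/10.
- Intercept model's variance: 37² × 4(1 − ICC)/(10m).
- Ratio R = (1 − f) + m × ICC × (1 − r)/(1 − ICC).
- Level of the nominal 5% test: 2[1 − Φ(1.96/√R)].

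Example with ICC 0.10, r = 0.8, f = 0: R = 1 + 50.49 × 0.10 × 0.2/0.90 = 2.122, giving 17.8%.

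Level (%) at r = 1 / 0.9 / 0.8:

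| ICC | f = 0 | f = 0.3 | f = 0.5 |
|---|---|---|---|
| 0.01 | 5.0 / 5.6 / 6.2 | 1.9 / 2.4 / 2.9 | 0.6 / 0.8 / 1.2 |
| 0.05 | 5.0 / 8.1 / 11.3 | 1.9 / 4.6 / 7.7 | 0.6 / 2.5 / 5.4 |
| 0.10 | 5.0 / 11.7 / 17.8 | 1.9 / 8.1 / 14.6 | 0.6 / 5.7 / 12.4 |
| 0.20 | 5.0 / 19.3 / 29.6 | 1.9 / 16.2 / 27.5 | 0.6 / 14.0 / 26.0 |

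**Step 3: break-even.** The level passes 5% only when r falls below 1 − f(1 − ICC)/(m × ICC). For ICC 0.01 / 0.05 / 0.10 / 0.20 this is 0.41 / 0.89 / 0.95 / 0.98 at f = 0.3, and 0.02 / 0.81 / 0.91 / 0.96 at f = 0.5.

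**Step 4: if a unit-by-period term is already intended.** Only the reference distribution is then open. Using z where t on 17 df applies gives 2 × P(t₁₇ > 1.96) = 6.7%.

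**Step 5: simulation.** REML intercept fits with blocked randomization and the Section 5.1 unit sizes (20,000 trials per setting) gave 5.9 / 11.7 / 18.8 / 31.0% at f = 0, r = 0.8, against 6.2 / 11.3 / 17.8 / 29.6% from the formula. A t-test on unit mean changes (18 df) held 4.5 to 5.2% in all 24 settings (f = 0 or 0.35). A separate run on 17 df, with 4,000 trials per setting, gave 4.0 to 5.5% (f = 0 or 0.3).

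**The case against.** The strongest reply is that the criticised model is not in the plan. No section says intercept or Wald, and the sizing uses a t-test. The Aim 2 detectable difference also rises with ICC, whereas an intercept-only contrast makes it fall (Step 1). That suggests some between-unit variation was meant to stay in the contrast. This stands. It does not settle what was intended, because the table's method is not stated and the table does not reproduce. If a unit-by-period term was meant, what is left is Step 4.

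A second reply is that the inflation rests on two quantities the documents do not give, and that repeat response is the likely case. This also stands. At f = 0.5 and ICC 0.05 the level is only 2.5% at r = 0.9 and 5.4% at r = 0.8. The large figures need ICC of 0.10 or more together with drift, and 0.20 is the top of a sensitivity range.

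The planned nurse covariates are not a general answer, since they help only so far as they explain drift. Simulations with three covariates unrelated to drift and independent responses still gave 12.6% (ICC 0.05, r = 0.8) and 17.6% (ICC 0.10, r = 0.8).

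A reader might infer that Aims 1 and 3 share the problem. The figures do not support that. For H1.2 an intercept Poisson model at r = 0.8 gave 5.1 / 4.4 / 6.2% at between-cluster CV 0.05 / 0.10 / 0.20. Adding a unit-by-period effect with t on 17 df gave 3.4 / 3.0 / 4.2%, further from 5% in two of the three settings. No inflation is claimed for Aim 3.

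**Conclusion.** The point holds as a conditional one for H2.1, and for H2.2 by the same wording. If Section 9.4.2 is fitted as a unit intercept with a Wald z test, the level is not controlled at 5%. It is liberal when units drift and the ICC is moderate or large, and conservative when nurses repeat and units do not drift. Over r = 0.8 to 0.9, ICC 0.05 to 0.20 and f = 0 to 0.5, it runs from 2.5% to 29.6%.

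A reader might infer that the plan specifies an invalid test or that inflation has been shown. The documents support neither: they do not state the structure, and they give no value for r or f. The formula also leaves out the preliminary three-way step test, so these are levels for the arm-by-period test alone. This is a cheap improvement to an open specification, not a demonstrated error.

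**What to change.** In Section 9.4.2, for Aim 2, specify one of the following:
- a mixed model with a random unit intercept plus a random unit-by-period effect, using Satterthwaite or Kenward-Roger degrees of freedom; or
- a regression of each unit's change in covariate-adjusted mean score on arm and step (20 units, 17 df), preferably weighted for unit size.

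In the change regression, keep the plan's step test as arm-by-step (16 df). Apply the chosen analysis within each imputed dataset before pooling. With many repeat respondents the mixed model stays conservative unless a nurse effect is added. The change regression does not, and it needs no nurse linkage. That is useful because Section 10.1.1.1 says the survey collects nothing identifiable while Section 10.1.9.1 calls the surveys individually identifiable.

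**Cost.** SAP wording only. At 8.6 points, ICC 0.05, no drift or overlap and equal units, the standard error is 3.21 and power goes from 76% (z) to 71% (t on 17 df). It is about 66 to 67% if the unequal units are left unweighted.

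95% half-widths at r = 0.8 with independent responses, in points:

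| ICC | Intercept model | Unit change, equal cells | Unit change, Section 5.1 sizes, unweighted |
|---|---|---|---|
| 0.01 | 6.4 | 7.3 | 7.7 |
| 0.05 | 6.3 | 8.4 | 8.8 |
| 0.10 | 6.1 | 9.6 | 9.9 |
| 0.20 | 5.8 | 11.7 | 11.9 |

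Much of the widening is uncertainty that the intercept model hides. Leave the Aim 1 models as they are, or add the extra term only as an optional sensitivity analysis. No change is asked for Aim 3.
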